**DOCUMENT DATE: October 25, 2022** 

## PART III. RESEARCH DESIGN & METHODS

# THE BLUE TEXT IN THE FOLLOWING SECTIONS IS A GUIDE TO ENSURE ALL RELEVANT INFORMATION IS INCLUDED IN YOUR APPLICATION. YOU MAY DELETE THE BLUE TEXT BEFORE SUBMISSION

1. **Introduction and Background.** *In reviewing the protocol, the IRB must consider the rationale for the study and the importance of the knowledge that may reasonably be expected to result.* 

Animal models and clinical studies show preliminary support for probiotic supplementation to ameliorate negative physiological consequences of heavy drinking, specifically inflammation. However, previous clinical trials have focused on alcohol-related complications, usually alcoholic liver disease. Such studies have been conducted in controlled settings with supervised abstinence from alcohol. As a result, it is not known whether probiotics improve alcohol-related inflammation in the absence of liver disease or in individuals who continue to drink heavily. The latter factor is important, as many individuals who currently are not seeking to cut down on drinking may nevertheless be willing to consume a dietary supplement to improve their health. In summary, probiotic therapy may be an acceptable intervention to reduce alcohol-related tissue injury in individuals not seeking to change their drinking behavior, but no clinical studies to date have addressed this population. This study will investigate effects of probiotics on inflammation in healthy heavy drinkers who currently are not seeking to change their alcohol use (i.e., are non-treatment-seeking).

2. Specific Aims and Study Objectives. The IRB must evaluate the objectives of the research in order to determine whether the risks to participants are reasonable in relation to the importance of the knowledge that may be gained.

This pilot project is a brief, open-label clinical trial of probiotics as an intervention to reduce systemic and neural inflammation in heavy drinkers. Heavy drinkers who do not yet show significant signs of liver disease also may stand to benefit from probiotics, but no clinical trials to date have addressed this population. This study will recruit 15 non-treatment-seeking heavy drinkers to complete an open-label within-subjects trial. Aim 1 is to demonstrate proof-of-concept for beneficial effects of probiotic use on inflammatory processes. Aim 2 is to examine effects of probiotic use on brain metabolites correlated with neuroinflammation using magnetic resonance spectroscopy. Aim 3 is to gather preliminary data on acceptability and feasibility of the probiotic intervention in non-treatment-seeking heavy drinkers.

- **Aim 1:** Demonstrate proof-of-concept for beneficial effects of probiotic use on inflammatory processes, as reflected in plasma markers of microbial translocation, immune activation, systemic inflammation, and liver function.
- **Aim 2:** Examine effects of probiotic use on brain metabolites correlated with inflammation using magnetic resonance imaging (MRI).
- **Aim 3:** Gather preliminary data on acceptability and feasibility of the probiotic intervention in the specific population of interest, i.e., non-treatment-seeking heavy drinkers.

If your study ONLY involves the use of identifiable secondary data / biospecimens, including coded data from which you may be able to ascertain participant identity, skip to PART V. Otherwise, please continue to next page.

v. 6/5/2020 Page **5** of **19** 

**3. Materials, Methods and Analysis.** The study design, methods and procedures must be adequately described in order for the IRB to understand all activities in which human subjects will participate. The IRB must also be able to differentiate those procedures that are performed for research purposes from those that are performed for routine care or evaluation.

The study will enroll participants to complete a brief open-label clinical trial of a probiotic dietary supplement. Individuals who provide informed consent and are eligible for participation will attend three study visits. At Visit 1, the research team will collect data on demographics, substance use, and medical history. Eligibility will be determined using the criteria listed below. Blood samples will be taken by a licensed healthcare provider. Eligible participants will complete a one-hour magnetic resonance imaging (MRI) scan, to occur on a separate day due to MRI scheduling constraints. Participants will receive a 30-day supply of the probiotic supplement with dosing and storage instructions. Participants will be instructed to take the standard dosage of 2 probiotic capsules per day. Participants will be asked to respond to a daily query from the research team confirming that they have taken their daily probiotic dose. Visit 2 will be scheduled 15 days (plus or minus 5 days) after the initiation of the probiotic supplement. The research team will collect blood samples and assess alcohol consumption since Visit 1, protocol adherence, and potential side effects. Participants will attend Visit 3 upon completion of the probiotic supplement, to occur 30 days (plus or minus 5 days) after initiation. Data will be collected as described for Visit 2, plus participants will complete a final one-hour MRI scan. Visit 4 will take place 1-10 months after completion of the study probiotic as a "washout" time point. A blood sample and substance use assessment will be collected at Visit 4. Appointments will take place at the Center for Alcohol and Addiction Studies lab space in the School of Public Health, and MRI scans will be conducted at Brown's Magnetic Resonance Imaging Facility (MRF).

Data to be collected at each session is described below.

- Visit 1 (Baseline Screening & MRI): Breath alcohol content (BrAC) will be measured using a handheld digital sensor to confirm BrAC of .00 g% at the time informed consent is obtained. Age, weight, pregnancy status, urine drug metabolites, recent alcohol use, treatment-seeking status, MRI safety/compatibility, safety for blood draw, basic medical history, and medication use will be assessed per Eligibility Criteria listed in Section 4. The research team will check the individual's state-issued photo ID to verify age and identity. Height and weight will be measured using a standard scale. Urine samples will be collected to test for presence of drug metabolites. Urine samples from participants who are able to become pregnant will be tested for pregnancy hormones. Basic demographic information, social history, and health-related data will be collected on questionnaires. Questionnaires on alcohol use and related symptoms (Alcohol Use Disorders Identification Test; AUDIT) will be administered. Blood samples will be taken for testing of biomarkers per the research aims. The Timeline Followback (TLFB) measure will be used to assess alcohol use in the past 30 days. Current or recent seeking of treatment for alcohol or drug use will be assessed. Participants will be interviewed for history of major medical conditions and current medication usage. Because it is necessary to confirm eligibility prior to MRI scanning and because advance notice is needed for MRI scheduling, participants will be asked to return on a separate day to complete a one-hour MRI scan of the brain at Brown's MRI Research Facility. Participants who are able to become pregnant will be given a urine pregnancy test prior to MRI scanning. BrAC of .00 g% will be confirmed prior to the MRI scan. Eligible participants will be given a 30-day supply of the probiotic supplement with dosing and storage instructions. The research team will collect contact information and request permission to send daily emails to confirm participants' adherence to the study protocol.
- Visit 2: Participants will complete questionnaires on side effects and adherence to the study protocol. Blood samples will be taken for testing of biomarkers. BrAC of .00 g% will be confirmed prior to study procedures.
- Visit 3 (Day 30 of Probiotic Intervention): The TLFB will be used to assess alcohol use since Visit 1. Side effects, adherence data, and blood samples will be collected as before. Participants who are able to become pregnant will be given a urine pregnancy test prior to MRI scanning. BrAC of .00 g% will be confirmed prior to the MRI scan. Participants will complete a one-hour MRI scan. They will be debriefed about the study and given the opportunity to ask questions at study completion.

v. 6/5/2020 Page **6** of **19** 

 Visit 4: A post-assessment visit will be conducted 1 to 10 months after completion of the probiotic. The Timeline Followback will be used to assess alcohol use in the past 30 days. A blood sample will be taken.

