### Procedures for a Positive Breath Alcohol Reading (BrAC):

In the event that a participant has a positive BrAC reading, the visit will be rescheduled for another date. If a participant has a repeated positive BrAC reading, the participant will be withdrawn from the study. If a participant's BrAC exceeds the legal limit for operating a motor vehicle (>.08%) at any visit, the person will be asked to wait at the research site until the BrAC reading is under .08%. The person will be offered a rideshare for transportation home at study expense.

**4. Participant Population.** In order to approve research, the IRB must determine that the selection of participants is equitable and reasonably related to the purpose and aims of the research. The IRB must also consider whether adequate safeguards are in place to minimize any risks that are unique to vulnerable populations. To make this determination, the IRB must review all methods and materials used to contact and recruit potential participants, including letters, flyers, emails, etc.

Human participants will be healthy, non-treatment-seeking adult heavy drinkers recruited from the community. Participants will not be asked or encouraged to change their alcohol use as part of the study. Up to 100 individuals will be enrolled to obtain a final sample of 15 individuals to complete the study. The sample size is appropriate for a pilot study intended to generate preliminary data for future full-scale work. Full eligibility criteria are listed below.

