#### STATISTICAL ANALYSIS PLAN

The goal of this analysis was to observe the effect of the probiotic on plasma concentrations of sCD14, sCD163, LBP, IL-6, IL-8, IL-10, MCP-1, and TNF-α. Of the 16 eligible participants who initiated the probiotic, 14 participants completed the probiotic course, and two were lost to follow-up prior to completion. Ten participants returned after the washout period for Visit 4. Descriptive statistics were obtained on demographic characteristics and drinking history. All collected datapoints were considered for analysis regardless of probiotic completion or loss to follow-up. Biomarker concentrations greater than three standard deviations from the mean were excluded to limit the impact of statistical outliers on the analysis. Regarding undetectable biomarker values, sCD14 had 3.7% missing data (n=2), IL-6 had 35% missing data (n=19), IL-10 had 5.6% missing data (n=3), LBP had 1.8% missing data (n=1), and MCP-1 had 5.6% missing data (n=3). There were no undetectable biomarker values for IL-8, sCD163, or TNF-α. Regarding outlier exclusions, IL-6 had one outlier value, IL-8 had two outlier values, LBP had one outlier value, sCD163 had one outlier value, and TNF-α had one outlier value. Distributions for sCD14, IL-10, and MCP had no outlier values.

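### Aim 1 and the SAP claim an effect of the probiotic from a single-arm study, and no model term is designated as the on-product versus off-product comparison

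*Combined protocol and SAP*

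**What the plan says.** The protocol (Part III, section 2) recruits participants "to complete an open-label within-subjects trial". Aim 1 is to "demonstrate proof-of-concept for beneficial effects of probiotic use on inflammatory processes", judged by plasma markers. The SAP opens in the same terms: "The goal of this analysis was to observe the effect of the probiotic on plasma concentrations".

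There is one pre-treatment blood sample (section 3, Visit 1). Visit 3 is at the end of the 30-day supply. Section 3 also gives a washout point: "Visit 4 will take place 1-10 months after completion of the study probiotic", and "A blood sample and substance use assessment will be collected at Visit 4".

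The SAP fits linear mixed models to Visits 1, 3 and 4.
- Model 1 (primary) examines the trajectory across the three visits, with a fixed intercept and slope and an autoregressive covariance. Its time-varying covariates are heavy drinking days, drinking days and days since the last drink.
- Model 2 (secondary) adds a quadratic time term to look for non-linear change.
- Model 3 repeats the analysis with undetectable values imputed.

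The SAP does not say whether time is coded as visit number, days or categories. It does not say which coefficient is the product effect, or what a return towards baseline at Visit 4 would mean.

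**The concern.** Without a concurrent control, any change after Visit 1 mixes the product effect with whatever else changes after entry. Candidates are regression to the mean in the markers, season, assay drift, and drinking changes that self-report misses. The covariates address self-reported drinking only.

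The Visit 4 sample is the one internal check on such shifts. A marker that falls on product and returns off product fits a product effect better than one that falls and stays down. For this check to count, an analysis has to be named for it and interpreted that way. A straight line through Visits 1, 3 and 4 does not do it: it responds most to a lasting shift of any cause and least to a reversible effect. At stake is what the pilot can tell the full-scale study it is meant to support.

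**Working it through.** **Plan's own figure.** The target is 15 completers, justified as "The sample size is appropriate for a pilot study intended to generate preliminary data for future full-scale work". No effect size, SD, alpha or power is given, so there is nothing to reproduce.

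**Inputs from the SAP.** 16 started, 14 completed, 10 returned for Visit 4; the models use Visits 1, 3 and 4.

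**Assumptions not in the documents.** Marker SD 1 at each visit; equal within-person correlation ρ of 0.5 or 0.7; two-sided 5% level, counting only results in the direction of benefit (nominal 2.5%); 10 participants with all three samples; no covariates.

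**Step 1: what a linear slope compares.** Least-squares weights are proportional to each time minus the mean time.
- Codes 1, 2, 3: (−1, 0, +1). Visit 3 has no weight.
- Codes 1, 3, 4: mean 8/3, deviations (−5/3, 1/3, 4/3), which scale to (−1, 0.2, 0.8).
- Days 0, 30, 330 (Visit 4 about 10 months later): mean 120, deviations (−120, −90, 210), which scale to (−0.57, −0.43, 1). A reversible fall at Visit 3 then pushes the slope upwards.

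**Step 2: what the quadratic term compares.** It is proportional to V3 − (a·V1 + b·V4), with a = (t4 − t3)/(t4 − t1) and b = 1 − a.
- Codes 1, 2, 3: a = b = 0.5.
- Codes 1, 3, 4: a = 1/3, b = 2/3.
- Days 0, 30, 330: a = 300/330 = 0.91, b = 0.09, close to V3 − V1.

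Model 2 therefore contains an on/off contrast, but its meaning depends on coding that the SAP does not state.

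**Step 3: chance of declaring benefit.** For weights w summing to zero, the SD of the contrast is √[(1 − ρ)·Σw²]. The noncentrality is δ√n/SD, where δ is the contrast's expected value, and the critical value is t(0.975, n − 1). Example: codes 1, 3, 4 with ρ = 0.5 give Σw² = 1.68 and SD = √0.84 = 0.917. A lasting 0.3 SD step gives δ = 0.2×0.3 + 0.8×0.3 = 0.3, noncentrality 0.3×3.162/0.917 = 1.04, probability 15.1%. A reversible 0.8 SD effect gives δ = 0.2×0.8 = 0.16, noncentrality 0.55, probability 7.2%.

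| Contrast | n | Lasting 0.3 SD non-product step (ρ 0.5 / 0.7) | Reversible 0.8 SD product effect (ρ 0.5 / 0.7) |
|---|---|---|---|
| Slope, equal spacing | 10 | 13.4% / 19.4% | 2.5% / 2.5% |
| Slope, codes 1, 3, 4 | 10 | 15.1% / 22.3% | 7.2% / 9.3% |
| V3 − V1 | 14 | 17.9% / 26.9% | 79.0% / 94.6% |
| V3 − (V1+V4)/2 | 10 | 7.1% / 9.3% | 73.9% / 91.7% |

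**Step 4: autoregressive errors, as the SAP selected.** With correlation ρ between successive visits and ρ² between Visits 1 and 4, generalised least squares keeps (−1, 0, 1) for equal spacing. For codes 1, 3, 4 it gives (−1, 0.33, 0.67) at ρ = 0.5 and (−1, 0.40, 0.60) at ρ = 0.7. The contrast SD is now √(w′Vw), V being the correlation matrix. For codes 1, 3, 4 at ρ = 0.5 it is √1.111 = 1.054, so the 0.3 step has noncentrality 0.90 and probability 12.5%. Over both codings and both ρ, the false signal is 10 to 17% and power for the reversible effect is 2.5 to 18%. The picture is unchanged.

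**Step 5: limits of the on/off contrast.**
- A lasting step of 0.3 contributes 0.15: it is halved, not removed.
- A product effect of 0.8 SD that persists through Visit 4 contributes 0.4, and power falls to 25.7% (ρ = 0.5) or 39.2% (ρ = 0.7).
- An adverse 0.3 SD shift at Visit 4 alone, with no change from Visit 1 to Visit 3, also contributes 0.15 and signals benefit in 7.1 to 9.3% of trials. V3 − V1 stays at 2.5%.

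**The case against.** The strongest reply is that the plan does use the off-product samples. Both models include Visits 1 and 4, and Model 2's quadratic term is algebraically an on/off contrast. This is correct. A reader might infer that no analysis uses the samples on both sides of treatment, and the SAP does not support that. What is missing is designation: the term is secondary, is presented as a curvature check, and is not tied to the product.

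A reader might also infer that any lasting shift would be credited to the product. That goes too far, because shifts acting through reported drinking are adjusted for. Nor do the documents show that such a shift would be reported as proof-of-concept, since the SAP gives no alpha or success rule.

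The 18 to 27% for V3 − V1 should not be read as the error rate of the plan, which contains no such test. It is shown only because that contrast is recommended below.

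One might instead want to allow effect wording whenever the on/off contrast excludes zero. Step 5 shows why not: its error under a lasting step is still 7 to 9%, and it takes in any shift at Visit 4.

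Finally, the study openly calls itself an open-label pilot, and the SAP is written in the past tense with completion counts. Both points are fair. Added contrasts must be labelled post hoc. Pilot status explains the sample size but does not supply the missing control.

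**Conclusion.** The concern holds in this form. The design identifies within-person change over time, while Aim 1 and the SAP goal state an effect of the probiotic, and no coefficient is designated as on-product against off-product.

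If Model 1's slope is linear in visit, which the added quadratic in Model 2 suggests but the SAP does not state, the primary term is poorly matched to the question. It gives a 13 to 22% false benefit signal for a lasting 0.3 SD shift not explained by reported drinking, and 2.5 to 9% power for a reversible 0.8 SD effect. These sizes rest on the assumed shift, effect and correlation. They also treat the analysis as a t-test on 10 complete cases, whereas the mixed model also uses incomplete cases and covariates. If visit was already fitted as a class factor, the slope problem disappears and the missing contrast specification and the causal wording remain.

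**What to change.** 1. Restate Aim 1 and the SAP goal as within-person change in the markers during 30 days of use.
2. Fit visit as a categorical factor. For each marker report, with 95% CIs, Visit 3 minus Visit 1 and Visit 3 minus the mean of Visits 1 and 4, marked as post hoc where they were not prespecified.
3. Describe a change that reverses at Visit 4 as consistent with a product effect, not as proof. Do not let an interval that excludes zero license effect wording.

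**Cost.** Revised wording and two contrasts on samples already collected. The on/off contrast leaves half of a lasting step in place, understates an effect that outlasts washout, and is exposed to season, assay drift and selective return at Visit 4, which falls 1 to 10 months later with 10 of 16 returning. That is why both contrasts should be shown, with the number of participants behind each.

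### The 30-day capsule supply does not cover the Visit 3 window, so a fully adherent participant can be sampled 5 to 6 days off product, and the models cannot identify such samples

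*Combined protocol and SAP*

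**What the plan says.** The supply and the visit schedule are in Part III, section 3 (Materials, Methods and Analysis):

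- Supply: "Participants will receive a 30-day supply of the probiotic supplement with dosing and storage instructions".
- Dose: "Participants will be instructed to take the standard dosage of 2 probiotic capsules per day".
- Visit 3 timing: "Participants will attend Visit 3 upon completion of the probiotic supplement, to occur 30 days (plus or minus 5 days) after initiation".
- The visit-by-visit list in the same section labels Visit 3 as "Day 30 of Probiotic Intervention" and adds: "Side effects, adherence data, and blood samples will be collected as before". The second MRI scan also belongs to this visit.

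Participants are also queried daily about whether they took their dose. Section 6 (Compensation / Reimbursement) pays for replies over a 30-day period.

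The Statistical Analysis Plan takes visit number (1, 3 and 4) as the repeated measure and describes a trajectory covering the time before, during and after use. Model 1 adjusts for three alcohol variables: heavy drinking days, drinking days, and time since the last drink. Model 2 adds a quadratic time effect. Model 3 changes only the handling of undetectable values. None of the three has a term for adherence, dosing status or time since the last capsule.

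**The concern.** A visit window is reasonable in itself. The gap is that the supply stops at 30 days while the window runs to day 35, and nothing bridges the difference.

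The Statistical Analysis Plan does not label its visits. Visit 1 is baseline and Visit 4 is the washout visit, so by inference Visit 3 is the only modelled point that stands for probiotic use. If some Visit 3 samples were drawn days after the last capsule, and if an effect fades within days, the change from Visit 1 to Visit 3 would be understated. Aim 1 is proof of concept for an effect on inflammatory markers, so a reader needs to know whether those samples were taken on product. The Visit 3 scan used for Aim 2 has the same timing problem, although the Statistical Analysis Plan covers only the blood markers.

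Late visits are foreseeable. The protocol reschedules a visit after a positive breath alcohol reading, and it mentions scheduling constraints for the scanner. The documents do not say how often either delayed Visit 3.

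**Working it through.** The documents give no figure of their own for this gap, so there is nothing to reproduce. The check is day arithmetic.

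**Inputs (protocol, section 3):** a 30-day supply; 2 capsules per day; Visit 3 at 30 ± 5 days after initiation.

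**Step 1: supply and window.** 30 × 2 = 60 capsules. Visit 3 may fall on days 25 to 35, which is 11 permitted days.

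**Step 2: last dosing day under full adherence.** The protocol does not say whether the first dose is day 0 or day 1. The day-30 label for Visit 3 suggests day 1; counting days after initiation suggests day 0.

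- First dose day 1: last dose on day 1 + 30 − 1 = 30.
- First dose day 0: last dose on day 0 + 30 − 1 = 29.

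**Step 3: days since last dose = visit day − last dosing day.**

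| Visit 3 day | First dose day 1 | First dose day 0 |
|---|---|---|
| 25 | 5 days of capsules left | 4 days of capsules left |
| 30 | 0 | 1 |
| 31 | 1 | 2 |
| 32 | 2 | 3 |
| 33 | 3 | 4 |
| 34 | 4 | 5 |
| 35 | 5 | 6 |

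A fully adherent participant is more than one daily dosing interval past the last capsule on 4 of the 11 permitted days (32 to 35) or on 5 of them (31 to 35).

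**Step 4: effect of missed doses.** Assume that misses are spread evenly and that the participant continues until the capsules run out. The last dosing day is then 30/adherence (first dose day 1) or 30/adherence − 1 (first dose day 0). At a day-35 visit, with negative gaps set to 0:

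| Adherence | First dose day 1 | First dose day 0 |
|---|---|---|
| 100% | 35 − 30.0 = 5.0 | 35 − 29.0 = 6.0 |
| 95% | 35 − 31.6 = 3.4 | 35 − 30.6 = 4.4 |
| 90% | 35 − 33.3 = 1.7 | 35 − 32.3 = 2.7 |
| 85.7% (30/35) | 0 | 1.0 |
| 83.3% (30/36) | 0 | 0 |

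For the supply to reach day 35, about 14% to 17% of doses would have to be missed. The better the adherence, the longer the possible gap.

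**Step 5: capsules needed to dose through day 35.** 35 × 2 = 70 if the first dose is day 1. 36 × 2 = 72 if it is day 0 and a dose on the visit day is wanted. That is 10 to 12 more than the 60 supplied.

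**The case against.** The strongest reply is that the plan ties Visit 3 to finishing the capsules as well as to the window. On that reading the ± 5 days is scheduling tolerance, and a late visit belongs to someone who missed doses and finished late; at 85.7% adherence the gap at day 35 is only 0 to 1 day. This accounts for a gap of 0 to 1 day, which is what an end-of-course sample should have. It does not override the stated window: day 35 remains permitted for someone who finished on day 29 or 30. At the other end, day 25 is permitted although a fully adherent participant still has capsules left.

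A second reply is that a fixed supply caps everyone at the same total dose, whereas a larger one lets exposure vary. That is a real trade-off but a small one. Under full adherence, the current window already allows sampling after anything from about 25 to 30 days of dosing.

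A third reply is that 5 to 6 days is short beside the 1 to 10 months before Visit 4, in an uncontrolled pilot with few participants. This stands as a limit on weight. It is a reason for a minor rating, and it does not show that the gap is harmless.

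A reader might go further and infer that the Visit 3 results are biased towards no effect, or try to state what share of the effect was lost. The documents do not support either. They give no Visit 3 dates, adherence results or fading rate. Any retained-effect percentage would rest wholly on an assumed half-life and an assumed spread of visit days, so none is given here.

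**Conclusion.** The point holds as a minor design gap. Under full adherence, the plan permits Visit 3 blood and imaging up to 5 days (first dose day 1) or 6 days (first dose day 0) after the last capsule, and none of the three models can tell such a sample from one taken on product.

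This rests on three things: no supply beyond 30 days, no instruction to dose until the visit, and the inference that Visit 3 is the modelled on-treatment point. The first two are absences from the documents, and the third is not stated outright.

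Whether any sample was affected is unknown. The Statistical Analysis Plan reports that 14 of the 16 who started completed the course, but not when they were seen relative to the last capsule. Understatement of an effect follows only if some visits were late and the effect fades within days. This is a possible dilution of undetermined size, not a demonstrated bias.

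**What to change.** **Future protocol.** Dispense 70 capsules (72 if the first dose is day 0 and a visit-day dose is wanted), instruct participants to dose until the day of Visit 3, and state which day the first dose is. The cost is 10 to 12 capsules per participant, and exposure at sampling would range over about 25 to 35 days.

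**Data already collected.**

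1. Derive the last-capsule date from the Visit 3 adherence data, supported by the daily queries. The queries may stop at day 30, given the 30-day payment period, so some dates may be uncertain.
2. Report the actual Visit 3 day and the days since last capsule.
3. If any Visit 3 sample was taken more than about 1 day (one dosing interval) off product, rerun Model 1 without those samples; if none was, say so. With at most 14 to 16 Visit 3 samples to start from, the rerun can show consistency but cannot settle the question.

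**Optional on-product check.** Report the Visit 1 to Visit 2 change beside the Visit 1 to Visit 3 change, if Visit 2 blood was assayed. The plan says "Visit 2 will be scheduled 15 days (plus or minus 5 days) after the initiation of the probiotic supplement", so that blood (days 10 to 20) falls within the supply. For alcohol adjustment, use the assessment that section 3 plans for Visit 2, if it was collected; otherwise run the comparison unadjusted. Visit 2 reflects only 10 to 20 days of use, so this supports the main result and does not replace it.

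For this trial the cost is one derived date per participant, one conditional rerun and, if wanted, one descriptive comparison.
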